6. STUDY PROCEDURES

6.1 Study Schedule

All required study procedures are outlined in Appendices A, B, and C. Additional patient visits may be scheduled if required for further evaluation of an abnormal laboratory value or a reported AE.

All reasonable attempts should be made to ensure compliance with the visit schedule and visit windows as outlined in Appendix A. However, in the event that a visit does not occur or is delayed, all subsequent visits should be calculated based on the time elapsed since the first dosing day in each Part of the study rather than from the date of the previous visit. Specifically, while patients are in the MAD, Part 1, of the study, all subsequent visits should be calculated based on the time elapsed since Day 1 in Part 1; once patients have entered the LTE, Part 2, of the study all subsequent visits should be calculated based on the time elapsed since Day 1 in Part 2.

6.1.1 Multiple Ascending Dose, Part 1

6.1.1.1 Screening Period (Week -8 to Week -1)

Written informed consent for the study will be obtained prior to the performance of any study-related procedures including screening procedures. During the Screening Period, inclusion/exclusion criteria will be evaluated to determine patient eligibility for the study. Abnormal laboratory screening results may be retested for review by the Study Medical Monitor for eligibility purposes. Personal information will also be collected including race, ethnicity, sex, and date of birth as part of the demographic information for all screened patients during the screening period.

6.1.1.2 Treatment Evaluation Period (Week 1 to Week 14)

Study Drug will be administered four times, with doses separated by 28 days (Section 8.1). In the event of a dosing interval change in Cohort D, Study Drug will be administered 2 times, with doses separated by 84 days.

Treatment Evaluation Period procedures are tabulated in Appendices A and C. Eligible patients will report to the Study Center on Day -1 (the day prior to first Study Drug administration) for assessments. Assessments should be completed at approximately the same time of day from visit to visit. At the completion of assessments on Day -1, patients will be discharged unless the Investigator feels it is in the patient's best interest for him/her to remain in the Study Center overnight. Patients will return to the Study Center on Day 1 to undergo CSF sampling and Study Drug administration via LP, followed by overnight observation in the Study Center, safety assessments on Day 2 and then discharge. On Day 3, the Study Center will conduct a brief visit with the patients by phone to capture any adverse events or changes in concomitant medication usage. On Day 8, the patients will return to the Study Center for additional assessments.

Each subsequent Study Drug administration will be conducted in the same manner, with most pre-dose assessments conducted on the day before Study Drug administration; post-dose, in-clinic observation of at least 6 hours after Study Drug administration (longer or overnight if deemed appropriate by the Investigator); in-clinic assessments on the day after Study Drug administration; telephonic contact with patients 2 days after Study Drug administration and in-clinic or telephonic assessments one week after Study Drug administration as defined in Appendix A.

6.1.1.3 Post-Treatment Period (Week 15 to Week 37) or Early Termination

After completion of the Treatment Evaluation Period, patients will enter the 23-week Post-Treatment Period. This period consists of 4-5 Study Center visits on Weeks 17, 21, 25, 29 (Cohorts C and D only), and 37, as outlined in the Schedule of Procedures in Appendix A.

Patients in Cohorts A and B will complete all visits up to Day 253 in Part 1 and will enter Part 2 of the study after the FSMG has reviewed the Part 1 Cohort C data during the dose-escalation meeting to Cohort D (2/3 of patients in Cohort C having received all doses of Study Drug in Part 1); therefore there will be a variable gap of time between the end of Part 1 and entry into Part 2 for those patients.

Patients in Cohorts C and D will seamlessly transition from Part 1 into Part 2 after completing all visits up to Day 253 in Part 1. The Part 1 Day 253 visit will correspond to the Part 2 Day -1 visit.

Patients who discontinue Study Drug in the Treatment Evaluation Period of Part 1 should complete any follow-up visits associated with the most recent administration of Study Drug (see Section 8.9) and should be encouraged to complete the Part 1 Post-Treatment Period. Patients who prematurely discontinue the Treatment Evaluation, or the Post-Treatment Periods, in Part 1, and patients whose treatment assignment has been unblinded during Part 1 due to a safety issue, will not be allowed to participate in Part 2.

6.1.2 Long-Term Extension, Part 2

6.1.2.1 Registration Period (Week -3 to Week -1)

This section is only applicable to patients from Cohorts A and B, as patients from Cohort C and D will seamlessly transition to Part 2.

Written informed consent will be obtained from patients in Cohorts A and B returning for LTE, Part 2, of the study prior to the performance of any study-related procedures. During the Registration Visit, inclusion/exclusion criteria will be evaluated to determine patient eligibility for the study. Any changes in medical history, and concomitant medications, that occurred between the end of Part 1 and entry into Part 2 will be recorded.

6.1.2.2 Treatment Evaluation Period (Week 1 to Week 48)

ISIS 814907 will be administered 5 times during the LTE, with doses given quarterly (84-day interval; Section 8.1).

The Part 2 Treatment Evaluation Period procedures are tabulated in Appendices A and C. Eligible patients will report to the Study Center on Day -1 (the day prior to first administration of ISIS 814907) for assessments. Assessments should be completed at approximately the same time of day from visit to visit. At the completion of assessments on Day -1, patients will be discharged unless the Investigator feels it is in the patient's best interest for him/her to remain in the Study Center overnight. Patients will return to the Study Center on Day 1 to undergo CSF sampling and ISIS 814907 administration via LP, followed by overnight observation in the Study Center, safety assessments on Day 2 and then discharge. On Day 3, the Study Center will conduct a brief visit with the patients by phone to capture any adverse events or changes in concomitant medication usage. On Day 8, the patients will return to the Study Center for additional assessments.

Each subsequent administration of ISIS 814907 will be conducted in the same manner, with most pre-dose assessments conducted on the day before administration of ISIS 814907; post-dose, in-clinic observation of at least 6 hours after administration of ISIS 814907 (longer or overnight if deemed appropriate by the Investigator); in-clinic assessments on the day after administration of ISIS 814907; telephonic contact with patients 2 days after administration of ISIS 814907 and in-clinic or telephonic assessments one week after administration of ISIS 814907 as defined in Appendix A.

6.1.2.3 Post-Treatment Period (Week 49 to Week 64) or Early Termination

After completion of the Treatment Evaluation Period, patients will enter the 16-week Part 2 Post-Treatment Period. This period consists of 2 Study Center visits on Weeks 60 and 64, as outlined in the Schedule of Procedures in Appendix A.

Patients who terminate early from the Part 2 Treatment Evaluation or Post-Treatment Periods (for reasons other than withdrawal of consent) should be encouraged to submit to additional visit(s) as described in detail in Section 8.9 (also see Appendices A and C and Study Design and Treatment Schema).

6.2 Study Assessments

The order of study assessments will be defined in the Study Manual. All efforts should be made to adhere to a consistent order of assessments throughout the study. Rest periods will be scheduled during the testing, and the patient should be permitted additional rest periods as needed to minimize testing fatigue.

6.2.1 International Standard Classification of Education (ISCED)

The ISCED is used to capture each patient's level of education based on categories ranging from pre-primary education through advanced degree programs.

6.2.2 Columbia Suicide Severity Rating Scale (C-SSRS)

The C-SSRS is a structured tool to assess suicidal ideation and behavior. Four (4) constructs are measured: severity of ideation, intensity of ideation, behavior and lethality of actual suicide attempts. Binary (yes/no) data are collected for 10 categories, and composite endpoints based on the categories are followed over time to monitor patient safety (Posner et al. 2011). It maps to the Columbia-Classification Algorithm for Suicide Assessment (C-CASA) and meets the criteria

listed in the recent FDA draft guidance for assessment of suicidality in clinical trials (FDA Sep 2010). The C-SSRS will be used to assess eligibility for the study and to monitor the patients throughout the study.

A referral for psychiatric evaluation is required for any increase (even if apparently transient) in the suicidal ideation score from baseline to a level that would have been exclusionary for this study. In any event of suspected active suicidal intent or significant suicidal behavior or clinical finding suggesting that the patient is dangerous to himself/herself, the patient should be referred for immediate psychiatric evaluation.

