On Part 2, Day 1, patients will be admitted to the Study Center, undergo pre-dose evaluations of vital signs and receive an IT bolus injection of ISIS 814907. All patients entering Part 2 must be kept at the Study Center for at least 24 hours following the first ISIS 814907 administration and undergo safety monitoring as scheduled. This 24-hour safety monitoring is required as it will not be known which patients received placebo in Part 1 and are therefore receiving ISIS 814907 for the first time in Part 2. For all subsequent administrations of ISIS 814907 in Part 2, the inpatient post-dose assessments may be reduced to a minimum of 6 hours. Assessments during these admission periods include neurological and physical examinations, vital signs, ECGs, blood sampling, and clinical laboratory analyses. Full standard neurological assessment (including fundi) will be performed 3 hours after dosing and prior to discharge from the Study Center.

ISIS 814907 administration in Part 2 will take place on Days 1, 85, 169, 253, and 337. During the Part 2 Treatment Evaluation Period, the patients will visit the Study Center at the times listed in the Schedule of Procedures - Part 2 (Appendix A). The Study Center will also monitor the patient's condition through scheduled telephone calls between visits.

CSF samples (approximately 20 mL each) will be taken pre-dose on each ISIS 814907 administration day during the Treatment Evaluation Period (Days 1, 85, 169, 253, and 337) and on Day 421 in the Post-Treatment Period. These CSF samples will be utilized for assessments of PK, tau protein, and other biomarker and laboratory analyses.

If a patient terminates early from the Part 2 Treatment Evaluation Period, he/she will be encouraged to return for the follow-up visits associated with their most recent administration of ISIS 814907 and for the Post-Treatment Period (Days 421-449).

Safety and Tolerability Evaluations

Patient safety will be monitored closely during the study by the Investigator and the FSMG. Further oversight of compliance with study safety procedures will be provided by the Ionis Medical Monitor.

Safety and tolerability evaluations include:

- Physical examination and standard neurological assessment (including fundi)
- Vital signs (HR, BP, orthostatic changes, weight)
- AEs and concomitant medications
- Columbia Suicide Severity Rating Scale (C-SSRS)
- CSF safety labs (cell counts, protein, glucose)

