8. TREATMENT OF PATIENTS

8.1 Study Drug Administration

Study Drug (ISIS 814907 or placebo) dosing will occur at the Study Center on Part 1 Days 1, 29, 57, and 85 for the 4-dose regimen, or Days 1 and 85 for the 2-dose regimen; in Part 2, ISIS 814907 dosing will occur on Days 1, 85, 169, 253, and 337. At each of these visits, the patient will undergo an LP procedure for collection of CSF (see Section 6.2.8) followed by a single IT bolus (2 minute) injection of Study Drug (ISIS 814907 or placebo) in Part 1 or ISIS 814907 in Part 2. A small gauge needle will be used, oriented with the opening rostral (toward the patient's head). The target site for needle insertion is the L3/L4 space but may be 1 segment above or 1-2 segments below this level, if needed.

Depending on institutional guidelines, local anesthesia may be used for the LP procedure. Sedation may not be used. Spinal ultrasound may be used for the LP procedure, if deemed necessary, but is not required. Fluoroscopy guidance may be used if attempts at LP without imaging are unsuccessful.

Table 2 outlines the dose equivalent and ISIS 814907 concentration for delivery for both the MAD and LTE parts of the study. See Section 3.1 for a description of adjustments that might be made to doses and the maximum dose that will be tested.

Table 2 Study Drug Dosing Information

| Cohort | Volume to Administer | Nominal ISIS 814907 Concentration | ISIS 814907 Per Dose* | | |
|--|---|-----------------------------------|-----------------------|--|--|
| Study Drug Dosing | Study Drug Dosing Information for the MAD, Part 1 | | | | |
| Cohort A (4-dose regimen) | 20 mL | 0.5 mg/mL | 10 mg or placebo | | |
| Cohort B (4-dose regimen) | 20 mL | 1.5 mg/mL | 30 mg or placebo | | |
| Cohort C (4-dose regimen) | 20 mL | 3.0 mg/mL | 60 mg or placebo | | |
| Cohort D (4-dose regimen) | 20 mL | 4.5 mg/mL | 90 mg or placebo | | |
| Cohort D (2-dose regimen) | 20 mL | 5.75 mg/mL | 115 mg or placebo | | |
| Study Drug Dosing | Information for the LTE | , Part 2 | | | |
| Cohorts A, B, and C (quarterly dosing) | 20 mL | 3.0 mg/mL | 60 mg | | |
| Cohort D (quarterly dosing) | 20 mL | 4.5 mg/mL | 90 mg | | |
| Or Cohort D (quarterly dosing) | 20 mL | 5.75 mg/mL | 115 mg | | |

The maximum dose level tested in a cohort will not exceed 115 mg

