Appendix A A.1. Schedule of Procedures – MAD Part 1, 4-Dose Regimen, Cohorts A and B Continued

| Study Period | Screen | | | | | | | Tr | eatn | | Evalu 3 We | | Peri | od | | | | | | | | Post | | ment Po /eeks) | eriod |
|---|--------------|----|----|----|----|-----|----|-----|------|----|---------------|----|------|----|----|-----|----|----|----|----|-----|-----------------|-----|-------------------|--------------------------|
| Week | -8 to -1 | | | 1 | | 2 | | 5 | | | 6 | | 9 |) | | 10 | | 1; | 3 | | 14 | 17 ¹ | 21 | 25 | 37 or ET ¹ |
| Day | -57 to -2 | -1 | 1 | 2 | 3 | 8 | 28 | 29 | 30 | 31 | 36 | 56 | 57 | 58 | 59 | 64 | 84 | 85 | 86 | 87 | 92 | 113 | 141 | 169 | 253 |
| Visit Window (days)* | - | | | 0 | | ± 3 | | ± 3 | 3 | | ± 3 | | ± | 3 | | ± 3 | | ± | 3 | | ± 3 | ± 3 | ± 7 | ± 7 | ± 7 |
| Visit Type ² | cl | cl | cl | cl | ph | cl | cl | cl | cl | ph | cl | cl | cl | cl | ph | ph | cl | cl | cl | ph | ph | cl | cl | cl | cl |
| Structural MRI, safety MRI (GRE T2 star, T2 FLAIR, T2 FSE/TSE, DTI) and ASL | х | | | | | | | | | | | | | | | | | | | | | | | X | |
| Imaging of CSF space | Х | | | | | | | | | | | | | | | | | | | | | | | | |
| FAQ, NPI-Q | Х | Χ | | | | | | | | | | | | | | | | | | | | Х | | Χ | Х |
| RBANS ⁹ | Х | Х | | | | | | | | | | Χ | | | | | | | | | | Х | | Х | Х |
| MMSE ⁹ | Х | | | | | | | | | | | Χ | | | | | | | | | | Х | | Х | Х |
| MHIS, CDR, GDS-SF | Х | | | | | | | | | | | | | | | | | | | | | | | | |
| C-SSRS | Х | Χ | Х | | | Х | Х | Х | Χ | | Х | Х | Χ | Х | | | Χ | Х | Χ | | | Х | Χ | Χ | Х |
| Serum/Plasma Biomarker Sample | | Х | | | | | Х | | | | | Х | | | | | Х | | | | | Х | Х | Х | Х |
| Thyroid Panel | Х | | | | | | | | | | | | | | | | | | | | | | | | |
| PT, INR, aPTT | Х | Χ | | | | | Х | | | | | Х | | | | | Χ | | | | | Χ | Х | Χ | Х |
| Archived Serum Sample ¹⁰ | | Х | | | | | Х | | | | | Х | | | | | Х | | | | | Х | Х | Х | Х |
| Drug/Alcohol Screen | Х | | | | | | | | | | | | | | | | | | | | | | | | |
| ECG (12-Lead, triplicate) | Х | Χ | | Χ | | | Χ | | | | | Χ | | | | | Χ | | | | | Χ | | | Х |
| Adverse Events | Х | Χ | Χ | Χ | Х | Х | Χ | Χ | Χ | Χ | Χ | Χ | Χ | Х | Χ | Χ | Χ | Χ | Χ | Х | Х | Χ | Х | Χ | Х |
| Prior/Concomitant Therapy/Procedures | Х | Х | Х | Х | Х | Х | Х | Х | Χ | Х | Х | Х | Х | Х | Х | Х | Х | Х | X | Х | Х | Х | Х | Х | Х |

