Appendix A A.2. Schedule of Procedures – MAD Part 1, 4-Dose Regimen, Cohorts C and D Continued

| Study Period | Screen | | | | | | | Tr | eatn | | Evalu 3 We | | n Peri | od | | | | | | | | F | Post-Ti (2 | reatme 23 Wee | | iod |
|---|--------------|----|----|----|----|-----|----|-----|------|----|---------------|----|--------|----|----|-----|----|----|----|----|-----|-----------------|---------------|------------------|-----|--------------------------|
| Week | -8 to -1 | | | 1 | | 2 | | 5 | | | 6 | | ę |) | | 10 | | 1 | 3 | | 14 | 17 ¹ | 21 | 25 | 29 | 37 or ET ¹ |
| Day | -57 to -2 | -1 | 1 | 2 | 3 | 8 | 28 | 29 | 30 | 31 | 36 | 56 | 57 | 58 | 59 | 64 | 84 | 85 | 86 | 87 | 92 | 113 | 141 | 169 | 197 | 253 ¹⁵ |
| Visit Window (days)* | - | | | 0 | | ± 3 | | ± ; | 3 | | ± 3 | | ± | 3 | | ± 3 | | ± | 3 | | ± 3 | ± 3 | ± 7 | ± 7 | ± 7 | ± 7 |
| Visit Type ² | cl | cl | cl | cl | ph | cl | cl | cl | cl | ph | cl | cl | cl | cl | ph | ph | cl | cl | cl | ph | ph | cl | cl | cl | cl | cl |
| Structural MRI, safety MRI (GRE T2 star, T2 FLAIR, T2 FSE/TSE, DTI) and ASL | х | | | | | | | | | | | | | | | | | | | | | | | х | | |
| FDG-PET or Tau PET ¹⁴ | Х | | | | | | | | | | | | | | | | | | | | | | | Х | | |
| Imaging of CSF space | Х | | | | | | | | | | | | | | | | | | | | | | | | | |
| FAQ, NPI-Q | Х | Χ | | | | | | | | | | | | | | | | | | | | Х | | Х | | Х |
| RBANS ⁹ | Х | Χ | | | | | | | | | | Х | | | | | | | | | | Х | | Х | | Х |
| MMSE ⁹ | Х | | | | | | | | | | | Х | | | | | | | | | | Х | | Х | | Х |
| MHIS, CDR, GDS-SF | Х | | | | | | | | | | | | | | | | | | | | | | | | | |
| C-SSRS | Х | Χ | Х | | | Х | Х | Х | Х | | Х | Х | Х | Х | | | Χ | Х | Х | | | Х | Х | Х | Х | Х |
| Serum/Plasma Biomarker Sample | | Х | | | | | Х | | | | | Х | | | | | Х | | | | | Х | Х | Х | Х | Х |
| Thyroid Panel | Х | | | | | | | | | | | | | | | | | | | | | | | | | |
| PT, INR, aPTT | Х | Χ | | | | | Х | | | | | Х | | | | | Χ | | | | | Х | Х | Х | Х | Х |
| Archived Serum Sample ¹⁰ | | Χ | | | | | Х | | | | | Х | | | | | Χ | | | | | Х | Х | Х | Х | Х |
| Drug/Alcohol Screen | Х | | | | | | | | | | | | | | | | | | | | | | | | | |
| ECG (12-Lead, triplicate) | Х | Χ | | Χ | | | Х | | | | | Х | | | | | Χ | | | | | Х | | | | Х |
| Adverse Events | Х | Χ | Χ | Χ | Х | Х | Х | Χ | Х | Х | Χ | Х | Х | Х | Х | Х | Χ | Х | Х | Х | Х | Х | Х | Х | Х | Х |

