Appendix A A.3. Schedule of Procedures – MAD Part 1, 2-Dose Regimen, Cohort D Continued

| Study Period | Screen | | | | Т | reatm | ent Ev (13 \ | aluatio Neeks | - | riod | | | | | | eatment 23 Weeks | | |
|--|--------------|----|----|----|----|-------|-----------------|------------------|----|------|----|----|-----|-----------------|-----|---------------------|-----|--------------------------|
| Week | -8 to -1 | | , | 1 | | 2 | 5 | 9 | | 1 | 3 | | 14 | 17 ¹ | 21 | 25 | 29 | 37 or ET ¹ |
| Day | -57 to -2 | -1 | 1 | 2 | 3 | 8 | 29 | 57 | 84 | 85 | 86 | 87 | 92 | 113 | 141 | 169 | 197 | 253 ¹⁵ |
| Visit Window (days)* | - | | (|) | | ± 3 | ± 3 | ± 3 | | ± | 3 | | ± 3 | ± 3 | ± 7 | ± 7 | ± 7 | ± 7 |
| Visit Type ² | cl | cl | cl | cl | ph | cl | cl | cl | cl | cl | cl | ph | ph | cl | cl | cl | cl | cl |
| Structural MRI, safety MRI (GRE T2 star, T2 FLAIR, T2 FSE/TSE, DTI) and ASL | Х | | | | | | | | | | | | | | | Х | | |
| FDG-PET or Tau PET ¹⁴ | Х | | | | | | | | | | | | | | | Х | | |
| Imaging of CSF space | Х | | | | | | | | | | | | | | | | | |
| FAQ, NPI-Q | Х | Χ | | | | | | | | | | | | Х | | Х | | Х |
| RBANS ⁹ | Х | Χ | | | | | | Х | | | | | | Х | | Х | | Х |
| MMSE ⁹ | Х | | | | | | | Х | | | | | | Х | | Х | | Х |
| MHIS, CDR, GDS-SF | Х | | | | | | | | | | | | | | | | | |
| C-SSRS | Х | Χ | Χ | | | Х | Х | Х | Х | Х | Х | | | Х | Х | Х | Х | Х |
| Serum/Plasma Biomarker Sample | | Χ | | | | | Х | Х | Х | | | | | Х | Х | Х | Х | Х |
| Thyroid Panel | Х | | | | | | | | | | | | | | | | | |
| PT, INR, aPTT | Х | Χ | | | | | Х | Х | Х | | | | | Х | Х | Х | Х | Х |
| Archived Serum Sample ¹⁰ | | Χ | | | | | Х | Х | Х | | | | | Х | Х | Х | Х | Х |
| Drug/Alcohol Screen | Х | | | | | | | | | | | | | | | | | |
| ECG (12-Lead, triplicate) | Х | Χ | | Χ | | | Х | Х | Χ | | | | | Χ | | | | Х |
| Adverse Events | Х | Χ | Χ | Χ | Х | Х | Χ | Х | Х | Х | Х | Х | Χ | Х | Х | Х | Χ | Х |
| Prior/Concomitant Therapy/Procedures | Х | Х | Х | Х | Х | Х | Χ | Х | Χ | Х | Х | Х | Х | Х | Х | Х | Х | Х |

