3.5.5 Columbia Suicide Severity Rating Scale (C-SSRS)

Per study design, the C-SSRS assessments will be scheduled in Part 1 and Part 2.

The C-SSRS collects binary Yes/No responses to 11 categories: five subtypes of suicidal ideation and five subtypes of suicidal behavior, and self-injurious behavior without suicidal intent. Specifically, the following outcomes are C-SSRS categories and have binary (Yes/No) responses. (The categories have been re-ordered from the actual scale to facilitate the definitions of the composite endpoints and to enable clarity in the presentation of the results (Nilsson et. al, 2013).

Suicidal Ideation:

Category 1 – Wish to Be Dead

Category 2 – Non-specific Active Suicidal Thoughts

Category 3 – Active Suicidal Ideation with Any Methods (Not Plan) without Intent to Act

Category 4 – Active Suicidal Ideation with Some Intent to Act, without Specific Plan

Category 5 – Active Suicidal Ideation with Specific Plan and Intent

Suicidal Behavior:

Category 6 – Preparatory Acts or Behavior

Category 7 – Aborted Attempt

Category 8 – Interrupted Attempt

Category 9 – Actual Attempt (non-fatal)

Category 10 – Completed Suicide

Other:

Category 11 – Non-suicidal Self-Injurious Behavior

A numerical score, the Suicidal Ideation Score, will be defined as the highest suicide ideation category (1–5) at which the patient responded "Yes" for the given visit. If the patient did not respond "Yes" to any of these categories, the score will be set to zero. The baseline suicidal ideation score will be summarized as baseline characteristics.

The C-SSRS will be analyzed for the MAD Period and LTE Period separately. For each of the categories above, the number and percent of patients with a "Yes" response at any time post-baseline (regardless of baseline response) will be summarized by treatment group. C-SSRS results will be listed for the MAD and MAD+LTE Periods. All data from patients with a "Yes" response at any time post baseline will be listed separately.

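### After the first LTE dose no C-SSRS is scheduled for 83 days; every other dose in the study is followed by one within a nominal 7 days

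*Combined protocol and SAP*

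**What the plan says.** Protocol Section 6.2.2 gives the scale two roles: "The C-SSRS will be used to assess eligibility for the study and to monitor the patients" during the study. It requires a psychiatric referral when the ideation score rises from baseline to a level that would have barred entry, including a rise that seems short-lived. Separately, it requires immediate referral when active suicidal intent is suspected or a clinical finding suggests danger to self.

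Dosing in Part 1 is on "Part 1 Days 1, 29, 57, and 85 for the 4-dose regimen, or Days 1 and 85 for the 2-dose regimen" (Section 8.1). For the extension, the synopsis states: "ISIS 814907 administration in Part 2 will take place on Days 1, 85, 169, 253, and 337".

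The assessment days are set only by the C-SSRS rows of Appendix A. Section 6.1.2.2 makes LTE Day 8 a clinic visit: "On Day 8, the patients will return to the Study Center for additional assessments". Appendix A.4 schedules a physical and neurological examination and adverse event collection at that visit, but no C-SSRS.

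The C-SSRS is a listed safety endpoint (protocol 10.1.1, SAP 1.3.1). SAP 3.5.5 states: "The C-SSRS will be analyzed for the MAD Period and LTE Period separately". For each category it counts patients with a positive answer at any post-baseline time.

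**The concern.** The protocol itself treats LTE Day 1 as a dose that needs extra care. The synopsis and Section 2.4.2 require at least 24 hours of observation because some patients will be having their first active dose. A footnote to Appendix A.4 adds that Cohorts A and B move to a higher dose than in Part 1. Yet this is the one dose after which the structured suicidality scale is not repeated soon.

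Two things are at stake. First, the score-based referral trigger in Section 6.2.2 can act only when a score is taken, so it has no planned opportunity to act between LTE Day 1 and Day 84. Second, SAP 3.5.5 will report LTE counts alongside Part 1 counts without saying that surveillance after the first dose differs between the two parts. A low LTE count could then be read as reassurance of the same quality.

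**Working it through.** **Inputs.** Dosing days are from protocol Section 8.1. C-SSRS days are read from the rows of Appendix A.1 to A.4 against their day headers. The number of cells matches the number of day headers in each table (25, 26, 18 and 26), so the blanks in A.4 are not a layout fault.

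**Formula.** Gap = day of next marked C-SSRS − dosing day (nominal days).

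| Schedule | Dose day | Next C-SSRS | Gap (days) |
|---|---|---|---|
| Part 1, 4-dose (A.1, A.2) | 1 | 8 | 8 − 1 = 7 |
| | 29 | 30 | 1 |
| | 57 | 58 | 1 |
| | 85 | 86 | 1 |
| Part 1, 2-dose (A.3) | 1 | 8 | 7 |
| | 85 | 86 | 1 |
| LTE (A.4) | 1 | 84 | 84 − 1 = 83 |
| | 85 | 86 | 1 |
| | 169 | 170 | 1 |
| | 253 | 254 | 1 |
| | 337 | 338 | 1 |

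LTE Day 1 is the only dose with a gap above 7 days. The windows do not change this: ±3 days gives 4 to 10 days for the Day 8 visit and 80 to 86 days for Day 84.

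**The LTE Day 1 mark does not fill the gap.** It carries no timing label, and in A.4 an unlabelled mark may be done at any time that day. SAP 3.2.3.2 takes the Day 1 pre-dose score into the baseline for late starters, so the mark cannot be counted on as a post-dose assessment.

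**A like-for-like case.** Cohort D receives 115 mg in both parts (SAP 1.1). Between the first dose and Day 84, A.3 marks a C-SSRS on Days 8, 29 and 57; A.4 marks none.

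**Patients affected, on planned cohort sizes of 8, 8, 12 and 16 at 3:1.**
- First active dose at LTE Day 1: 2 + 2 + 3 + 4 = 11 former placebo patients.
- Higher dose than in Part 1: 6 + 6 = 12 active patients from Cohorts A and B, who go from 10 or 30 mg to 60 mg.
- Together 11 + 12 = 23 of 44. This is an upper limit on the planned numbers, because not everyone need enter the LTE.

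**After the change.** With a C-SSRS at LTE Day 8 the gap becomes 8 − 1 = 7 days, as after the first Part 1 dose.

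**The case against.** The strongest reply is that one scale is not the whole of monitoring. A reader might infer that patients go without early suicidality monitoring after this dose, and the documents do not support that. Patients stay at least 24 hours, or 6 hours with a next-day return under the COVID-19 provision. Adverse events are collected on Days 2, 3 and 8. Neurological examinations, which cover mental status (Section 6.2.5), are done on Days 1, 2 and 8. Referral on clinical suspicion needs no score. This part of the reply stands.

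A reader might also infer that a transient effect could never show in the late-start columns. That goes too far. The documents do not state the recall period of the post-baseline C-SSRS, and if it asks about the time since the last assessment, Day 84 would cover Days 1 to 84. An event reported as an adverse event would also enter the adverse event tables.

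A third tempting reading is that the C-SSRS tables are biased between early and late starters. The SAP does not plan the comparison this would need. Part 1 and the LTE are analysed separately, the assessment schedule is shared by all groups within each part, and SAP 3.2.1 does not list the C-SSRS among the Active Treatment Period endpoints. Setting early starters' first active dose against late starters' is a contrast that a reader would have to build.

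Finally, the lighter LTE schedule may be deliberate. LTE Day 92 is also a clinic visit without a C-SSRS, whereas Part 1 Day 36 had one, and no text demands a C-SSRS after every dose. But the dose before Day 92 already has a C-SSRS on Day 86, so that omission leaves no comparable gap. No reason is given for leaving Day 8 blank.

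**Conclusion.** The gap is real and confined to one dose: 83 nominal days to the next scheduled C-SSRS after LTE Day 1, against 7 or 1 after every other dose. It falls on the dose that is a first active exposure for up to 11 planned patients and a dose increase for up to 12 more. The consequence is lower sensitivity, not blindness. Transient ideation may be missed, or may rest on recall over about 12 weeks (83 ÷ 7 = 11.9) in patients with mild AD, and the score-based referral trigger lies idle meanwhile. The gap creates no between-group bias in the planned within-period tables. The limit is on reading LTE counts as equivalent early surveillance to Part 1.

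This rests on nominal visit days, planned cohort sizes with full entry to the LTE, and a recall period that the documents leave unstated. The documents supplied report no suicidality signal for the drug, so the point is an inexpensive improvement in safety ascertainment rather than evidence of harm.

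**What to change.** In Appendix A.4, mark the C-SSRS at the existing LTE Day 8 clinic visit, matching Part 1 Day 8. If the omission is intended, give the reason in the protocol.

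In SAP 3.5.5, add a sentence that for patients already past that visit the first scheduled post-dose LTE C-SSRS is Day 84, so LTE counts of positive answers do not reflect the same early surveillance as those from Part 1. State the recall period used at post-baseline visits in the same place.

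The cost is one short questionnaire per patient at a visit that already takes place, one mark in the schedule and a few lines in the SAP.
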